8.2 Data collection

Designated investigator staff will enter the data required by the protocol into the OC/RDC system. Designated investigator site staff will not be given access to the system until they have been trained.

Automatic validation procedures within the system check for data discrepancies during and after data entry and, by generating appropriate error messages, allow the data to be confirmed or corrected online by the designated investigator site staff. The Investigator must certify that the data entered into the electronic Case Report Forms are complete and accurate. After database lock, the investigator will receive copies of the patient data for archiving at the investigational site.

Prior to the final database lock, CSR I ([Section 3.5](#)) will be prepared. The database for this CSR will consist of:

- All data in all patients up to 26 weeks (Visit 207)
- Data for the subset of patients who have completed 52 weeks treatment plus follow up (Visit 214 and 301) or prematurely withdrawn from the study.

- Data up to last available visit for patients who have already completed 26 weeks (Visit 207) but have not yet completed 52 week treatment plus follow up (Visit 214/301)

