16.1.9.3	Assessment windows, baseline and post-baseline definitions, missing data handling.....	39
16.1.9.3.1	Data pooling and assessment windows.....	39
16.1.9.3.2	Baseline measurements.....	39
16.1.9.3.3	Post-baseline measurements.....	41
16.1.9.4	Laboratory parameters – direction of interest and definition of clinically notable values.....	42
16.1.9.5	Vital signs and ECG – definition of clinically notable values.....	44
16.1.9.6	Statistical methodology and assumptions.....	45

Amendment 1

This amendment of the statistical analysis plan (SAP) is largely based on the changes made in the Clinical Trial Protocol Amendment 5 (released 17-Jan-2018). The rationale of the major changes in protocol is provided in the following.

Amendment Rationale

Conduct primary analysis after all patients have completed at least 26 weeks treatment:

An interim database freeze will be conducted to perform the primary analysis. The database for primary analysis will contain all data up to the Data Lock Point (DLP), which is defined as the date when all patients complete Week 26 (V207) assessments or withdraw from the study. For patients who are ongoing at the time of interim database freeze, the database will include all data available until the last completed visit.

Primary analysis includes primary and key secondary endpoints as well as other pre-specified endpoints at Week 26. [REDACTED]

Safety data will also be summarized.

In terms of reporting, two separate clinical study reports (CSRs) will be written. CSR 1 will base on the interim database freeze and CSR 2 on the final database lock. A dedicated unblinded team will be involved in CSR 1 related activities. In order to maintain the integrity of the study data, a separate blinded team will continue the study until its completion.

Modification of analysis of key secondary endpoint, ACQ-7:

The key secondary objective has been modified to demonstrate the superiority of add-on indacaterol (QAB149) 150 µg by demonstrating superiority of QMF (150/160 and 150/320 µg combined) to mometasone furoate doses (MF, 400 µg and 800 µg combined) in terms of Asthma Control Questionnaire (ACQ-7) after 26 weeks of treatment. The add-on effect of indacaterol will be tested only if the individual treatment comparisons are significant for the primary endpoint (i.e., there is evidence of efficacy of both doses of QMF over respective MF doses in terms of lung function).

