Sample size is re-calculated based on updated analysis and multiplicity adjustment. As a result, a more modest sample size is needed to establish efficacy while providing sufficient safety exposure for QMF149. Assuming 10% dropout, the calculation shows that the sample size of 2000 patients (i.e., 400/arm) will provide 94% power for primary endpoint trough FEV₁ and 85% power for key secondary endpoint ACQ-7.

1 Introduction

This document contains details of the statistical methods that will be used in the phase III clinical trial CQVM149B2301. This study is designed to evaluate the efficacy and long term safety of two different doses of QMF149 (QMF149 150/160 µg and QMF149 150/320 µg via Concept1) over two respective mometasone furoate (MF) doses (i.e., total daily doses of MF 400 µg and MF 800 µg via Twisthaler®) in poorly controlled asthmatic patients as determined by pulmonary function testing and effects on asthma control.

Data will be analyzed according to Section 9 of the study protocol. The primary analysis will be conducted using all data up to the Data Lock Point (DLP), which is defined as the date when all patients have completed the assessments after at least 26 weeks of treatment (Visit 207) or prematurely withdrawn from the study. In particular for efficacy analysis, each patient's data until the last available study visit (scheduled or unscheduled) prior to the DLP will be included. For safety analysis, data up the DLP will be included too. This will include all planned analyses presented in this SAP.

Two separate CSRs will be published:

- Primary Analysis CSR: To support analyses once all patients have completed the assessments at least 26 weeks of treatment (Visit 207) or prematurely withdrawn from the study.
- Full CSR: To support analyses once all patients have completed the assessments after 52 weeks of treatment (Visit 214) plus follow-up (Visit 301) or prematurely withdrawn from the study.

This SAP is valid for analyses of both CSRs.

Important information is given in the following sections and details are provided, as applicable, in [Appendix 16.1.9](#).

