2.4 Study medication

2.4.1 Duration of exposure

Duration of exposure to study treatment will be calculated as the number of days starting from the first dose date up to and inclusive the last dose date (ignoring the duration when study treatment may have been interrupted). The duration of exposure will be summarized by treatment for the safety set as a continuous variable with the standard descriptive statistics. In addition, the duration of exposure will be summarized with total patient years and the number (%) of patients who were exposed to study drug for each 1 - 29 days, 30 – 86 days, 87 – 183 days, 184 – 254 days, 255 – 365 days, and > 365 days.

In the interim analysis, patients who are ongoing at the time of interim database freeze will be considered as exposed until the DLP.

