2.6.2.7 Asthma exacerbations

All analyses will base on data as reported on the "Asthma Exacerbation Episodes" eCRF.

In patients with multiple exacerbations, if the start date of an exacerbation was less than 7 days after the end date of a previous episode, then this will be assumed to be one continuous exacerbation with the start date taken from the first episode and the end date from the second or last episode. The worst severity of these episodes will be taken as the severity of the collapsed exacerbation. Collapsing of exacerbation episodes will only be done for efficacy analyses but not for safety analyses of adverse events which includes asthma exacerbations.

Asthma exacerbations starting after the first dose and not later than one day after the date of last dose will be included in the analyses of efficacy.

The following asthma exacerbation-related parameters will be summarized considering the whole 52 weeks of double-blind treatment. The analysis will be performed by exacerbation

category wherever specified. The exacerbation categories are: All (mild, moderate, severe), the combination of moderate or severe, and severe.

The annual rate of asthma exacerbations, by exacerbation category

The (annual) rate of asthma exacerbations will be analyzed using a generalized linear model assuming the negative binomial distribution including treatment, age (12 to 17, ≥ 18 years), region and history of asthma exacerbation in the 12 months prior to screening (Yes, No) as fixed-effect factors, and FEV₁ prior to inhalation and FEV₁ 15 to 30 min post inhalation of salbutamol/albuterol (components of SABA reversibility) as covariates. The log exposure in years will be used as an offset variable in the model (see Section 2.4.1 for the definition of exposure). The estimated rate ratio along with two-sided 95% interval and corresponding p-value will be provided.

Time to first asthma exacerbation, by exacerbation category

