Time-to-event variables will be analyzed using a Cox regression model stratified by age (12 to 17, ≥ 18 years). The model will include treatment, region and history of asthma exacerbation in the 12 months prior to screening (Yes, No) as fixed-effect factors, and FEV₁ prior to inhalation and FEV₁ 15 to 30 min post inhalation of salbutamol/albuterol (components of SABA reversibility) as covariates. For treatment comparisons the estimated adjusted hazard ratio will be displayed along with the associated two-sided 95% confidence interval and corresponding p-value. Kaplan-Meier analysis stratified by treatment group will be also presented and displayed graphically. Patients without an event will be considered as censored at the earliest date of (last treatment + 1, death, last visit). In the interim analysis, patients without an event who are ongoing at the time of interim database freeze will be censored at the DLP. For patients having an event, the start date of the exacerbation will be considered to calculate the time to event (i.e., the number of days from start of treatment up to the event start date).

Time to first hospitalization for asthma exacerbation (only for severe exacerbations possible)

The analysis is similar to time to first asthma exacerbation.

Time to permanent discontinuation of study drug due to asthma exacerbation

The analysis is similar to time to first asthma exacerbation.

Duration of asthma exacerbations in days, by exacerbation category

The duration of asthma exacerbations is defined as the sum of days per patient over all exacerbations and the respective lengths (from start to end date). This will be analyzed for treatment group differences using the van Elteren test stratified for age (12 to 17, or ≥ 18), region and history of asthma exacerbation in the 12 months prior to screening (Yes, No).

Total amounts (in doses) of oral corticosteroids used to treat asthma exacerbations

Total amount (in prednisone-equivalent mg doses) of oral corticosteroid used to treat asthma exacerbations during the 52 week treatment period will be summarized descriptively by treatment group.

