2.9.2 Primary analysis after all patients have completed at least 26 weeks treatment

The primary and key secondary endpoints of CQVM149B2301 study are the trough FEV₁ and ACQ-7 after 26 weeks of treatment, respectively while the entire study treatment period is 52 weeks. In order to support a marketing authorization filing once all patients have completed 26 weeks of treatment (V207) or prematurely withdrawn from the study, an interim database freeze will be conducted to perform the Primary Analysis.

The database for Primary Analysis will contain data up to 26 weeks for all patients and data up to 52 weeks for patients who have completed the study. For patients who are ongoing at the time of interim database freeze, the database will include data available until last completed visit.

Primary analysis includes primary and key secondary endpoints as well as other pre-specified endpoints at Week 26. [REDACTED]

At the time of interim database freeze for Primary Analysis, a limited number of pre-specified Sponsor members will be unblinded to the study data to work on study and submission related activities which require knowledge of these data.

The study will continue under the management of a separate blinded team who will be responsible for study conduct from the time of the 26 week interim database freeze until end of study. In order to maintain the integrity of the study data, the blinded team members will not have access to any of the unblinded data or results. In addition, all patients and investigators will remain blinded.

Two separate CSRs will be published:

- Primary Analysis CSR: To support analyses once all patients have completed the assessments after 26 weeks of treatment (Visit 207) or prematurely withdrawn from the study. This will include analysis of primary and key secondary as well other pre-specified endpoints which are evaluable at this time.
- Full CSR: To support analysis once all patients have completed the assessments after 52 weeks of treatment (Visit 214) plus follow up (Visit 301) or prematurely withdrawn from the study.

Since the analysis of primary and key secondary objectives will be performed only for the Primary Analysis CSR, the interim analysis will not require any adjustment to the overall type I error rate.

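### Week 26 analysis: exacerbation events of ongoing patients stop at the last visit, but time at risk runs on to the data lock point

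*SAP*

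**What the plan says.** **Data cut.** SAP Section 1 sets separate cuts for the Week 26 analysis. For efficacy, each patient's "data until the last available study visit (scheduled or unscheduled) prior to the DLP will be included". For safety, "For safety analysis, data up the DLP will be included too". The Amendment 1 rationale says that for ongoing patients "the database will include all data available until the last completed visit", and Section 2.9.2 that "the database will include data available until last completed visit". Protocol Section 8.2 gives the same rule for patients who are past Week 26 but not finished.

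**Exacerbations are efficacy.** SAP Section 2.6.2.7 treats them so and sets an onset window: "Asthma exacerbations starting after the first dose and not later than one day after the date of last dose will be included". Section 1 puts all planned SAP analyses into the Week 26 report, so these are included.

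**Time at risk.** The negative binomial offset is log exposure as defined in Section 2.4.1, where "patients who are ongoing at the time of interim database freeze will be considered as exposed until the DLP". Appendix 16.1.9.6 adds one day. For Cox and Kaplan-Meier, the general rule in Section 2.6.2.7 censors at the earliest of last treatment plus one day, death and last visit. The interim rule then says that "patients without an event who are ongoing at the time of interim database freeze will be censored at the DLP", without the last-visit limit.

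**The concern.** A rate needs events and person-time over the same interval. Here the events of an ongoing patient end at the last visit, while the person-time ends at the DLP. An exacerbation between the two enters the efficacy data only if it brings the patient in for an unscheduled visit before the DLP. If it does not, the patient is counted as at risk and event-free over time from which no event could be counted. This pulls down the annual rates and the Kaplan-Meier incidence after about Day 183.

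The reports could also disagree internally. Exacerbations are adverse events too (SAP Section 2.7.2) and safety data run to the DLP, so one report could count an episode as an adverse event and leave it out of the efficacy rate. SAP Section 2.9.2 says that this database freeze is meant to support a marketing authorization filing.

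**Working it through.** The documents state no exacerbation rate, event count or accrual period, so there is no figure of the plan to reproduce. The check sizes the mismatch.

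**Inputs from the documents.** Protocol Table 6-1 places contacts from Week 26 on at Days 183, 197, 225, 254, 281, 309, 337 and 364, clinic and telephone, with exacerbations reviewed at each. The assumed dropout is 10% (Protocol Section 9.8, SAP Section 2.10). There are about 400 patients per arm. The DLP falls when the last patient has completed Week 26.

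**Assumptions.** Accrual is uniform over 26 to 156 weeks. The 10% leave by Week 26 (on average at Day 91.5) and none leave later. The event rate is constant. Where counts are shown, it is 0.5 per year.

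**Mean gap for an ongoing patient.** The intervals L between contacts are 14, 28, 29, 27, 28, 28 and 27 days, which sum to 181. Mean gap = ΣL² / (2ΣL) = 4847 / (2 × 181) = 13.4 days. Mean follow-up of ongoing patients is (183 + 364)/2 = 273.5 days, so the gap is 13.4/273.5 = 4.9% of their person-time.

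**All patients, 52-week (364-day) accrual.**
- Ongoing share: 0.9 × 181/364 = 0.448.
- Gap per randomised patient: 0.448 × 13.4 = 6.0 days.
- Mean exposure: 0.9 × (0.497 × 273.5 + 0.503 × 364) + 0.1 × 91.5 = 296 days.
- Gap share: 6.0/296 = 2.0%.

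Understatement = gap share × (1 − proportion of gap events captured):

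| Accrual (assumed) | Ongoing | No capture | 50% captured | 80% captured |
|---|---|---|---|---|
| 26 weeks | 89% | 4.7% | 2.3% | 0.9% |
| 52 weeks | 45% | 2.0% | 1.0% | 0.4% |
| 78 weeks | 30% | 1.3% | 0.6% | 0.3% |
| 104 weeks | 22% | 0.9% | 0.5% | 0.2% |
| 156 weeks | 15% | 0.6% | 0.3% | 0.1% |

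With full capture it is zero. If dropout continues at the same rate after Week 26, the no-capture figures fall slightly (52 weeks: 1.95%). If only clinic visits counted as visits, the mean gap would be about 47 days and the no-capture figure 3% to 16% overall for 24 down to 6 months of accrual. Table 6-1 numbers the telephone contacts as visits, so the smaller figures are the natural reading.

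**Events per arm, 52-week accrual.** 400 patients give about 325 patient-years. 325 × 0.5 = 162 events, of which 2.0%, about 3, fall in the gap. The Poisson 95% limits on 162 events are about ±1.96/√162 = ±15%.

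**Kaplan-Meier** (simulated, 52-week accrual, hazard 0.5 per year, continuing dropout):

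| | One common cut-off | As planned, no capture | As planned, 80% captured |
|---|---|---|---|
| Day 183 | 22.2% | 22.2% | – |
| Day 300 | 33.7% | 33.2% | 33.6% |
| Day 360 | 38.9% | 38.1% | 38.8% |

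**Treatment comparison.** The gap depends on calendar time and on a visit schedule common to all arms. In a negative binomial and Cox simulation (12-month accrual, no capture), aligning the cut-offs moved an estimated control rate from 0.486 to 0.496 per year. The rate ratio stayed at 0.704 and the hazard ratio at 0.738. Even with 6% versus 14% dropout between arms, the rate ratio shifts by only 0.3%, 0.1% and 0.05% at 26, 52 and 104 weeks of accrual.

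**The case against.** The strongest reply is that the text can be read the other way. The Amendment 1 rationale and SAP Section 1 both also say that the primary analysis uses all data up to the DLP. Only Section 1 has a cut specific to efficacy. Section 2.6.2.7 draws on the exacerbation eCRF and selects episodes by onset relative to dosing, not by visit. A patient still on treatment at the DLP has not passed the last dose, so the onset window would admit a gap event. On that reading, events, offset and censoring share one boundary and there is no bias. Moreover, if the database itself stopped at the last visit, gap episodes could not appear as adverse events either, so the disagreement between tables needs Section 1 to be applied literally.

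This does not remove the mismatch. Each all-data sentence is narrowed by a more specific one that follows it, and an onset window does not bring back records that the cut has excluded. Nothing in either document says that exacerbations after the last visit are complete and counted as efficacy. At best the SAP contains two rules, and the programmer would have to choose.

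The rest of the objection concerns size, and much of it stands. E-diary alerts should prompt calls, visits and eCRF entries (Protocol Section 6.4.4), so partial capture is likely. The 26-week scenario is improbable. Amendment 4 (14 February 2017) widened eligibility and Amendment 5 (released 17 January 2018) cut the sample size, which suggests recruitment over at least most of the intervening 48 weeks. Exacerbations lie outside the alpha-controlled family, and Protocol Section 9 has the final report update the results.

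**Conclusion.** The mismatch holds as written, and it is small. In the Primary Analysis report, absolute exacerbation rates could be understated by up to about 2% at an accrual of 52 weeks or longer, and by 0.4% or less if 80% of gap events are captured. The corresponding Kaplan-Meier shortfall at Day 360 (52-week accrual) is at most about 0.8 percentage points. These figures rest on assumed uniform accrual, a constant event rate and telephone contacts counting as visits. They are well inside sampling error, and the effect is zero with full capture.

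Rate ratios and hazard ratios are essentially unaffected. The primary and key secondary tests do not use these data, and no patient is ongoing at the final analysis. The case for acting is that the rule is internally inconsistent, the report is meant for a filing, and the repair costs almost nothing.

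**What to change.** For ongoing patients in the Week 26 exacerbation analyses, state one cut-off for events, offset and censoring that does not depend on the outcome.

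- **Preferred:** include every episode on the exacerbation eCRF with onset up to the DLP, and keep exposure and censoring at the DLP. This needs those pages to be complete to the DLP, which the safety cut already implies.
- **Fallback, only if the pages will not be complete:** end events, offset and censoring at the last scheduled Table 6-1 contact, clinic or telephone, on or before the DLP. This gives up about 2.0% of person-time at 52-week accrual (0.9% at 104 weeks) and any later event.
- **Avoid** ending follow-up at an unscheduled visit that an exacerbation triggered. Follow-up would then depend on the outcome, and the rate could be overstated by up to about 2% (52-week accrual).

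Reconcile the Amendment 1 rationale, Section 1 and Section 2.9.2 of the SAP with the chosen rule. The cost is SAP wording and one date rule in the interim derivations, best settled before the interim freeze. The final report does not change.

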2.6.2.8 Quality of life as assessed by Asthma Quality of Life Questionnaire (AQLQ)

AQLQ is a 32-item disease specific questionnaire designed to measure functional impairments that are most important to patients with asthma, with a recall time of two weeks and each question to be answered on a 7-point scale (1-totally limited/problems all the time, 7-not at all limited/no problems). It consists of 4 domains:

- Symptoms = Mean of Items 6, 8, 10, 12, 14, 16, 18, 20, 22, 24, 29, 30 (12 items)
- Activity limitation = Mean of Items 1, 2, 3, 4, 5, 11, 19, 25, 28, 31, 32 (11 items)
- Emotional function = Mean of Items 7, 13, 15, 21, 27 (5 items)
- Environmental stimuli = Mean of Items 9, 17, 23, 26 (4 items)
- Overall Score = Mean of Items 1 to 32 (32 items)

[name], developer of AQLQ questionnaire suggests no more than 10% of missing data. This means that for a questionnaire of 32 items, no more than 3 items should be missing. Further, for the activity and symptom domains, the recommendation is no more than 1 missing value per domain, and for the emotional function and environmental stimuli domains, no missing responses at all. Missing individual items will be imputed similarly to missing items for ACQ-7.

For the overall score and each respective domain score, treatment group comparisons will be performed using the same MMRM model as specified for the primary analysis with baseline AQLQ as covariate. The post-baseline visits are scheduled for Weeks 4, 12, 26, 36, and 52.

The proportion of patients who achieve an improvement in the AQLQ (i.e., an increase in the AQLQ overall score of ≥ 0.5 from baseline) at post-baseline visits will be analyzed using the same logistic regression model via GEE as specified for the ACQ-7 analysis except that baseline AQLQ will be used instead of the baseline ACQ-7. The handling of missing data will also be the same as for ACQ-7, i.e., first missing continuous AQLQ values will be imputed using a MI method under MAR assumption. Then continuous AQLQ values will be converted into binomial responses and GEE method will be used to analyze the datasets and then the results from GEE method will be combined for the inference.

